7.5.3 Handling of Missing Efficacy Data

Missing data in this study may result from patients discontinuing from the study prematurely or missing intermediate visits or selected assessments while remaining on study. Every reasonable effort will be made to obtain the protocol-required data for all study assessments that are scheduled for all patients who have been enrolled.

For mixed model repeated measures (MMRM) efficacy analyses, which assumes that data are missing at random (MAR), missing observations will not be imputed.

MAR refers to missingness that is independent of missing responses, conditionally on observed responses and covariates. As the imputation strategy should always consider the dropout patterns and the time-course of the efficacy measurements by treatment, the pre- and post- withdrawal values will be assessed to understand the impact of dropouts on the efficacy results. Two additional methods of sensitivity analyses will be performed to compare the results from an MAR-based analysis versus an MNAR-based analysis under several MNAR scenarios. The first method is the return-to-baseline using Multiple Imputation in which patients with missing data known or believed to have discontinued protocol therapy were assumed to return to its baseline value and not derive any benefit from treatment. The second method is the Tipping Point Analysis, which assumes that patients from the experimental treatment arm who discontinue treatment or initiate a rescue therapy would have values worse by some amount “delta” compared to efficacy values of similar patients who continue with study treatment and do not require rescue. The detailed analysis plan and implementation of these methods are described in Section 7.5.3.1 and 7.5.3.2.

Last observation carried forward (LOCF) will also be used to handle missing data as described in Section 7.1.1.3 for analyses such as sensitivity analyses of Hb1Ac (ANCOVA) at week 52 and 156.

7.5.3.1 Model for Change from Baseline Based on Return-to-Baseline Multiple Imputation

The return-to-baseline MI (Multiple Imputation) imputes the change from baseline to Week 52, and samples will be drawn from a Normal distribution with mean 0 and variance of pooled data. Let $X = (X_{\text{obs}}, X_{\text{miss}})$ be the complete data at Week 52. X is consisted of observed measurements X_{obs} and the missing observations X_{miss} . In return-to-baseline imputation, when X is change from baseline (CHG), each missing observation X_{miss} is imputed by a random draw from a Normal distribution with mean 0 and variance v_{imp} :

$$X_{\text{mis}} \sim N(0, v_{\text{imp}}),$$

The variance v_{imp} is calculated from the observed changes:

$$v_{\text{imp}} = (1 + 1/N_c) v_c,$$

where v_c is the variance of the change among completers across all treatment arms, and N_c is the number of completers.

An ANCOVA model will be used to analyze the imputed datasets for change from baseline with treatment group as a fixed factor and Baseline HbA1c as a covariate. The least square mean (LS mean) estimates will be combined using Rubin's combination rules for statistical inference. All available measurements will be used including observations post-rescue and post-discontinuation of treatment.

In this study, the primary analysis is comparing Dapagliflozin + Saxagliptin + Metformin group to control group Glimipiride + Metformin. The above approach will be conducted using the Glimipiride + Metformin as the control group.

7.5.3.2 Tipping Point Analysis based on Model for Change from Baseline Using Multiple Imputation

In order to address the impact of missing data due to initiation of rescue therapy, or premature treatment discontinuation on the primary efficacy analysis, a Tipping Point Analysis using multiple imputation will be performed to compare the results from analysis assuming a missing at random (MAR) mechanism versus analysis assuming a missing not at random (MNAR) mechanism. The specific MNAR assumption that will be considered in this framework is that patients from the experimental treatment arm who discontinue study treatment prematurely or who initiate a rescue therapy would have, on average, their efficacy values post-rescue/post-treatment discontinuation worse by some amount δ compared to efficacy values of similar patients who continue with the study treatment and do not require rescue therapy. δ is considered to be a sensitivity parameter representing a degree of departure from the MAR assumption. The aim of the Tipping Point Analysis is to find a "tipping point" corresponding to a value of δ where the study conclusion of a significant treatment effect would no longer hold. An interpretation of clinical plausibility of the assumption underlying the tipping point will be provided.

The tipping point approach based on multiple imputation of values at time points after treatment discontinuation or initiation of rescue can be performed with a specified adjustment (referred to as δ adjustment or shift) applied to values imputed under an MAR-based imputation model for the appropriate subset of patients. In order to find a tipping point, a series of imputations will be performed with increasing values of δ .

For the primary endpoint which is a continuous variable, we will use an additive δ adjustment (a shift) as follows:

$$Y_{j(adj)}^{(m)} = Y_{j(imp)}^{(m)} + \delta$$

where -

- $Y_{j(\text{imp})}^{(m)}$ are values imputed using a MAR-based imputation model in the m^{th} imputed dataset, $m=1, \dots, M$ (number of imputations)
- δ is a mean shift (delta adjustment) parameter for adjusting imputed values

The main steps in the implementation of the Tipping Point Analysis are described below.

Step 1: Use the common Step 1 in Section 4.1.5.1 for partial imputation to get monotone missing pattern.

Step 2: Impute remaining monotone missing data using an MAR-based regression imputation model for all patients who discontinued study treatment prematurely or initiated a rescue therapy. Apply a shift (an additive delta adjustment) to imputed values of patients in the experimental treatment arm (Dapagliflozin + Saxagliptin + Metformin). The variables used as explanatory variables for imputation include Treatment, HbA1c baseline, and post-baseline HbA1c at each time point.

Imputations with delta adjustment described above will be performed with varying values of delta in order to perform a series of analyses with progressively larger values of delta until a tipping point is reached. A tipping point will correspond to the smallest value of delta for which the primary hypothesis is no longer rejected.

Step 3: At each level of delta, analyze each of multiple imputed datasets using the same MMRM model as used for the primary analysis. Combine estimates obtained from multiple imputed datasets based on Rubin's combination rules.

Step 4: Using a 2-sided Type I error level of 0.05, find the tipping point, i.e., the value of delta parameter for which the primary hypothesis is no longer rejected. In this study, we will compare Dapagliflozin + Saxagliptin + Metformin vs. Glimepiride + Metformin for each delta value. We will find the delta value at which the test of hypothesis is no longer rejected. A clinical interpretation about the plausibility of the assumptions underlying the tipping point will be provided.

7.5.4 Secondary Efficacy Analyses

In order to protect the overall type I error rate, the interpretation of the statistical significance of treatment comparisons for each secondary efficacy endpoint will be done using a step-wise procedure as outlined in Section 7.5.1

The ordered list of secondary endpoints for the sequential testing procedure is:

- Mean change from baseline in total body weight at Week 52.
- Percent of subjects achieving a therapeutic glycemic response, defined as HbA1c < 7.0%, at Week 52.
- Mean change from baseline in SBP at Week 52.

- Time to treatment intensification (addition of insulin or other glucose-lowering agent for rescue therapy or discontinuation for lack of glycemic control) during the 52-week double-blind treatment period.
- Time to treatment intensification (addition of insulin or other glucose-lowering agent for rescue therapy or discontinuation for lack of glycemic control) during the 156-week treatment period.
- Proportion of subjects achieving a therapeutic glycemic response, defined as HbA1c < 7.0%, at Week 156

The analysis of change from baseline for total body weight and SBP will be performed using the same longitudinal repeated measures model as for the primary efficacy endpoint.

The proportion of subjects achieving a therapeutic glycemic response (defined as HbA1c < 7.0%) at Week 52 and Week 156 will be summarized by treatment group and compared between treatment groups using logistic regression, adjusting for baseline Hb1Ac. The 95% confidence intervals for the response rate within each treatment group, as well as for the difference in response rates between treatment groups, will be calculated with adjustment for baseline HbA1c. Subjects who are rescued, discontinued or have missed measurements at Week t (t = 52 and 156, respectively) will be considered as not achieving glycemic response.

Time to treatment intensification will be analyzed using a Cox proportional hazards model. Estimates of the hazard ratio and 95% confidence intervals will be provided. This analysis will be performed only when there are at least 10 events in each treatment group. Kaplan-Meier estimates will be calculated and plotted by treatment group. For the analysis during 52 / 156 weeks, all subjects will be censored at 52 / 156 week short-term / long-term treatment period if treatment intensification has not occurred by then. Subjects rescued at Week 52 / 156 visit will be counted as having an event for the analysis.

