3.3.1 Inclusion Criteria

1. Signed Written Informed Consent

- a) Subjects (or designee) must be willing and able to give signed and dated written informed consent.

2. Target Population

- a) Subjects with T2DM with inadequate glycemic control, defined as a central laboratory HbA1c $\geq 7.5\%$ and $\leq 10.5\%$ obtained at the screening visit.
 - i) Note: The proportion of subject with HbA1c 7.5 % - 8.5 % will be capped at 40%.
 - ii) Note: At Week -2 (Lead-In), a qualification check will be performed and subjects will be included if their FPG is ≤ 270 mg/dL. A re-test will be permitted within 7 days if the initial result was > 270 mg/dL but < 300 mg/dL. Subjects will be excluded if the mean value of the Week -2 (Lead-In) result and the re-test result is > 270 mg/dL.
- b) Subjects should be taking the same daily dose of metformin ≥ 1500 mg for at least 8 weeks prior to the enrollment visit and must not take any other antihyperglycemic therapy for more than 14 days (consecutive or not) during 12 weeks prior to screening.
- c) BMI 20.0 to 45.0 kg/m² (inclusive) at the enrollment visit.
- d) Subject Re-enrollment: This study permits the re-enrollment of a subject who has been discontinued from the study as a pre-treatment failure (ie, subject has not been randomized / has not been treated). If re-enrolled, the subject must be re-consented.

Inclusion criteria at randomization (Visit 3, based on laboratory results from Visit 2):

- a) FPG ≤ 270 mg/dL (≤ 15 mmol/L).

For inclusion in the MRI-PDFF sub-study and/or CGM sub-study, subjects must fulfill the following criteria:

- b) Provision of informed consent for the MRI-PDFF and/or CGM sub-study.
- c) BMI 20.0 to 40.0 kg/m² (inclusive) at the enrollment visit and upper weight of 140 kg max (MRI-PDFF sub-study only).

If a subject declines to participate in the MRI-PDFF sub-study or CGM sub-study, there will be no consequences for the subject's participation in the main study. The subject will not be excluded from other aspects of the study described in this Clinical Study Protocol, as long as proper consent is obtained.

3. Age and Reproductive Status

- a) Males and females, aged ≥ 18 years old at the time of the screening visit.
- b) Women of childbearing potential (WOCBP) must have a negative serum or urine pregnancy test (minimum sensitivity 25 IU/L or equivalent units of HCG) within 24 hours prior to the start of study drug.
- c) Women must not be breastfeeding

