3.5.2 Rescue Guidelines for Subjects with Protocol-Defined Lack of Glycemic Control

During the course of the trial, subjects may be eligible for the addition of open-label rescue medication to their blinded treatment regimen in order to treat ongoing hyperglycemia. Insulin is recommended as the first-line rescue therapy, as subjects will already be taking dual or triple-therapy (based on their randomization assignment). If a subject refuses treatment with insulin or is not a candidate for insulin, other options for rescue therapy can be considered. However, initiation of a DPP4 inhibitor, SGLT2 inhibitor, or SU is not permitted for rescue therapy. The sub-sections and tables listed below define the lack of glycemic control criteria for initiation of rescue medication in both short-term and long-term periods of the study.

Pre-specified glycemic criteria (see Table 3.5.2-1), based upon central laboratory HbA1c, FPG, and repeat confirmatory FPG were established during the treatment period; to determine eligibility for open-label rescue medication, FPG is to be used from Week 9 to Week 52, and HbA1c after Week 52 to Week 156.

Table 3.5.2-1: Lack of Glycemic Control Criteria for Initiation of Rescue Medication

Visit Label	Central Laboratory FPG/HbA1c
Week 9	FPG > 270 mg/dL (15.0 mmol/L)
After Week 9 to Week 16 (including Week 16)	FPG > 240 mg/dL (13.3 mmol/L)
After Week 16 to Week 28 (including Week 28)	FPG > 220 mg/dL (12.2 mmol/L)
After Week 28 to Week 52 (including Week 52)	FPG > 200 mg/dL (11.1 mmol/L)
After Week 52 to Week 156	HbA1c > 7.5%

Subjects with a central laboratory FPG value meeting the lack of glycemic control criterion at a pre-specified visit will be scheduled for a follow-up visit (within 3 - 5 days) to obtain a second central laboratory FPG value and review the subject's glucose meter readings.

If the repeat central laboratory FPG value still meets the criterion, the subject must be rescued. Subjects who meet rescue criteria in the blinded treatment period must first complete the Rescue Visit procedures before receiving open-label rescue medication to ensure that important trial endpoint measurements are collected.

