7.1.2 Longitudinal Repeated Measures Analysis

A longitudinal repeated measures analysis using “direct likelihood” will be performed. The SAS procedure PROC MIXED will be used. The preferred model will include the fixed categorical effects of treatment, week, and treatment-by-week interaction as well as the continuous fixed covariates of baseline measurement and baseline measurement-by-week interaction.

The following general model will be used:

$$C_{ijk} = \text{intercept} + \beta_1 [M_{\text{baseline},ij}] + \tau_i + \alpha_k + (\alpha \tau)_{ik} + (\alpha M_{\text{baseline}})_{ijk} + \text{error}_{ijk}$$

(Model 7.1.2.1)

where:

C_{ijk} is the change from baseline for subject j in treatment group i at time k ,

β_1 is the slope coefficient for the baseline measurement,

$M_{\text{baseline},ij}$ is the baseline measurement of subject j in treatment group i ,

τ_i is the mean effect of treatment group i ,

α_k is the mean effect at time k

$(\alpha \tau)_{ik}$ is the interaction term between treatment group i and time k .

$(\alpha M_{\text{baseline}})_{ijk}$ is baseline measurement-by-week interaction term for subject j in treatment group i at time k , and

error_{ijk} is the error term for subject j in treatment group i at time k .

An unstructured matrix for the within-subject error variance-covariance will be used. The denominator degrees of freedom will be calculated according to the Kenward-Roger method.

In case of non-convergence of the preferred model or memory space issues, the following back-up models are defined:

- The first backup model is the same as the preferred model, but the Kenward-Roger method will be replaced by Satterthwaite approximation.
- The second backup model is the same as the preferred model but without the term for baseline measurement-by-week interaction.

The second back-up model will only be provided if the first back-up model does not converge or has memory issues.

If the models do not converge, then the spatial power covariance matrix will be used instead.

The model will provide least-squares mean estimates, standard errors, and 2-sided 95% confidence intervals for mean change at all time points within and between treatments.

Appropriate diagnostics will be performed to check model assumptions.

Assessment of Treatment-by-Baseline Interaction:

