7.1.8 Proportion of Subjects Achieving Pre-defined Characteristic

Unless otherwise specified, the proportion of subjects with a pre-defined characteristic at Week t will be analyzed using logistic regression with adjustment for baseline HbA1c value. Subjects in the randomized treatment group who do not demonstrate achieving therapeutic glycemic response at a specified timepoint or are rescued will count as treatment failures from that timepoint. When proportion of responders (e.g., meeting HbA1c criteria) is needed, the estimates, confidence intervals, and tests will be obtained using this methodology with adjustment for baseline variable (e.g., adjustment for baseline HbA1c). For each treatment group, the probability of response is first modeled using a logistic regression model with baseline (e.g., baseline HbA1c) as a covariate.

When there are less than 5 responders in any treatment group, the unadjusted (and difference in) proportions, exact 95% confidence interval, and p-values from the Fisher's exact test (when applicable) will be provided.

For composite response endpoints (glycemic control without hypoglycemia or weight gain), the proportion of subjects achieving targets will be summarized by treatment group without adjustment for baseline.

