7.5 Efficacy

7.5.1 Overall Efficacy Summary

All efficacy analyses will be performed using the Randomized Subjects data set. In addition, at the ST analysis, the primary efficacy analysis will be performed using the Evaluable Subjects data set if > 10% of subjects in any treatment group have relevant protocol deviations.

Unless otherwise specified, all analyses will be done using values prior to rescue/intensification of treatment or treatment discontinuation (plus a tolerance window after last dose as detailed in Section 0). For the endpoint of the proportion of subjects achieving a therapeutic glycemic response at Week 52/Week 156, all available data will be used, but subjects rescued prior to Week 52/Week 156 will be treated as non-responders.

The comparator (glimepiride plus metformin) will be tested against saxagliptin, in co-administration with dapagliflozin plus metformin, for the primary efficacy endpoint at the alpha = 0.05 level (two-sided). The secondary efficacy endpoints will then be tested sequentially, each comparison tested at the alpha = 0.05 level (two-sided). The following testing hierarchy (shown in order of the step-wise testing sequence) for treatment comparisons will be used:

- Mean change from baseline in HbA1c at Week 52 (primary endpoint).
- Mean change from baseline in total body weight at Week 52.
- Percent of subjects achieving a therapeutic glycemic response, defined as HbA1c < 7.0%, at Week 52.
- Mean change from baseline in systolic blood pressure (SBP) at Week 52.
- Time to treatment intensification (addition of insulin or other glucose-lowering agent for rescue therapy or discontinuation for lack of glycemic control) during the 52-week double-blind treatment period.

If all the above five comparisons performed for the short-term analysis are statistically significant, the following two comparisons will be tested sequentially for the short-term plus long-term analysis:

- Time to treatment intensification (addition of insulin or other glucose-lowering agent for rescue therapy or discontinuation for lack of glycemic control) during the 156-week treatment period.
- Proportion of subjects achieving a therapeutic glycemic response, defined as HbA1c < 7.0%, at Week 156

Analyses of exploratory endpoints specifically designed for sub-studies (CGM and MRI-PDFF) will be performed using the subsets of the Randomized Subjects data set for the sub-studies.

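### The Cox model for time to treatment intensification (steps 5 and 6 of the hierarchy) names no baseline covariate; adding baseline HbA1c would recover a modest amount of power

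*SAP*

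**What the plan says.** Time to treatment intensification is the time to starting a rescue agent or to stopping because glycaemia is not controlled. It is fifth (52 weeks) and sixth (156 weeks) in the fixed sequence of SAP 7.5.1 and Protocol 8.4.2. Each step is tested at two-sided 0.05. The 52-week test gates both Week 156 tests.

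SAP 7.5.4: "Time to treatment intensification will be analyzed using a Cox proportional hazards model". A hazard ratio, its 95% interval and Kaplan-Meier curves follow, and the model is fitted only if each arm has at least 10 events. Protocol 8.4.2.2 and the synopsis use the same sentence without naming any term.

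The other confirmatory steps are explicit:

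- Steps 1, 2 and 4 (HbA1c, weight, SBP) use the repeated-measures model of SAP 7.1.2, with "continuous fixed covariates of baseline measurement and baseline measurement-by-week interaction".
- Steps 3 and 7 (responders at Weeks 52 and 156) are "compared between treatment groups using logistic regression, adjusting for baseline Hb1Ac".

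On the rescue trigger, Protocol 3.5.2 states: "FPG is to be used from Week 9 to Week 52, and HbA1c after Week 52 to Week 156". Entry requires a screening HbA1c of 7.5% to 10.5% (Protocol 3.3.1), with the note that "The proportion of subject with HbA1c 7.5 % - 8.5 % will be capped at 40" per cent.

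**The concern.** No other section supplies the missing terms. SAP 7.1.7, the general section on time-to-event data, covers only Kaplan-Meier estimates and Greenwood intervals. The default in SAP 7.1.8, "will be analyzed using logistic regression with adjustment for baseline HbA1c value", applies to proportions. Protocol 8.4.7 adds interaction terms to the original time-to-event model for subgroup tests but does not say what that model contains.

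Baseline HbA1c is a natural predictor here. The lower entry limit equals the long-term rescue threshold of 7.5%, so baseline HbA1c measures how far a subject must fall to stay clear of rescue after Week 52. It is already collected and already used in the primary and responder models.

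Leaving a prognostic covariate out of a Cox model moves the estimated treatment effect toward no effect. At stake is some power at two controlled steps, and a confirmatory test whose terms would otherwise be chosen at programming.

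**Working it through.** **1. The plan's own figure.** The only power statement (SAP 5, Protocol 8.1) concerns HbA1c change: difference 0.35, SD 1.1, 220 per arm, 5% not evaluable, 90% power.

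- Evaluable per arm: 220 × 0.95 = 209.
- Power = Φ(0.35 / (1.1 × √(2/209)) − 1.960) = Φ(3.253 − 1.960) = Φ(1.293) = 0.902.
- Required n = 2 × 1.1² × (1.960 + 1.282)² / 0.35² = 207.6, so 208 evaluable; 208 / 0.95 = 219 per arm, against 220 stated.

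It reproduces. There is no counterpart for time to intensification.

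**2. Direction.** Let the hazard be h(t) = h₀(t) exp(β·treatment + γ·baseline). If γ ≠ 0 and baseline is omitted, high-risk subjects leave the risk set faster in the arm with the higher hazard. The arms then become unlike over time and the fitted treatment coefficient is closer to 0 than β. If β = 0 this does not occur, so the test's size is kept. In 3,000 simulated null trials the rejection rate was 5.4% with and without the covariate.

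**3. Size under the plan's rescue limits.** Simulated trials, 800 per scenario, 220 per arm.

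- From the documents: FPG and HbA1c limits of Protocol Table 3.5.2-1, baseline range 7.5% to 10.5%, 40% of subjects below 8.5%, HbA1c difference 0.35.
- Assumed: an alternative difference of 0.2, conversion of HbA1c to FPG, slope of follow-up on baseline 0.3 to 0.5, between-subject SD 0.8 to 1.0, mean reduction 1.0 to 1.4, drift and dropout.

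Results for a difference of 0.35, unadjusted → adjusted:

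| Reduction / slope / SD | 52-week HR | 52-week power (%) | 156-week HR | 156-week power (%) |
|---|---|---|---|---|
| 1.0 / 0.3 / 1.0 | 0.696 → 0.689 | 62.6 → 64.0 | 0.731 → 0.725 | 75.6 → 76.9 |
| 1.4 / 0.3 / 1.0 | 0.665 → 0.666 | 55.6 → 56.8 | 0.706 → 0.701 | 76.6 → 77.9 |
| 1.0 / 0.5 / 1.0 | 0.705 → 0.697 | 58.9 → 63.0 | 0.738 → 0.728 | 73.8 → 79.9 |
| 1.4 / 0.5 / 1.0 | 0.676 → 0.668 | 53.5 → 55.1 | 0.710 → 0.699 | 75.2 → 78.5 |
| 1.0 / 0.5 / 0.8 | 0.673 → 0.663 | 66.9 → 71.8 | 0.707 → 0.694 | 87.7 → 91.0 |
| 1.4 / 0.5 / 0.8 | 0.638 → 0.630 | 59.3 → 62.5 | 0.671 → 0.654 | 87.6 → 92.2 |

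With the six scenarios at a difference of 0.2 included, the change in power was −0.1 to +4.9 points at 52 weeks and +0.2 to +6.1 points at 156 weeks. The hazard ratio moved away from 1 in 23 of 24 comparisons. Monte Carlo error is about 1 to 2 points, so the low end cannot be told from zero. Events in the glimepiride arm averaged about 60 to 90 of 220 by Week 52 and 130 to 164 by Week 156.

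**4. Wider check.** Proportional-hazards data, 440 subjects, 1,500 trials per scenario, true hazard ratio 0.4 to 0.75:

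| Control event rate | Gain, baseline HR per SD 1.3 to 1.6 | Gain, baseline HR per SD 2.0 to 2.7 |
|---|---|---|
| 10% to 30% | +0.3 to +3.7 points | +1 to +11 points |
| 50% to 85% | +0.4 to +10 points | +10 to +32 points |

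The threshold scenarios in step 3 implied a baseline hazard ratio per SD of only 1.2 to 1.7.

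**The case against.** The strongest reply is that silence is not a decision. A reader might infer that the plan chose an unadjusted model and knowingly gave up power. The text does not say so; it simply lists no terms. That stands, but it does not remove the point: a confirmatory model without listed terms is either unadjusted or open, and the same sentence settles both.

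A reader might also infer that the unadjusted test is biased or invalid. It is not. Its size holds, and the attenuation is the difference between a marginal and a conditional hazard ratio. The marginal one also matches the Kaplan-Meier display.

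A third inference is that tied event times could cost about ten points. With times held in visit weeks, a true hazard ratio of 0.70 and 35% to 60% of controls having the event at Week 65, power was 69% to 77% under Breslow against 81% to 87% under Efron. With times in days the difference was under 1 point. The plan adopts neither visit-week times nor Breslow, and no document says that long-term events cluster at Week 65. Rescue may start up to 2 weeks after the criteria are met and visits have a ±5-day window, which favours times in days.

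Other objections stand in part. Before Week 52 the trigger is FPG, so baseline FPG is a reasonable alternative covariate there. The event includes discontinuation for lack of control, which is not a pure threshold, and after Week 52 HbA1c sets eligibility for rescue. The treatment-assignment sections are redacted, so stratification, and any protection against chance imbalance, cannot be judged. Finally, SAP Version 3 (1 October 2019) follows work on the short-term report, and SAP 2.3.1 has the short-term database unblinded for reporting, so timing limits what can still be changed.

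**Conclusion.** The point holds as a modest, inexpensive improvement to two confirmatory steps. Baseline HbA1c is absent from the stated Cox model although it is prognostic by the design of the rescue rules and is used in the primary and responder models. With treatment alone in the model, type I error is kept, the hazard ratio is slightly attenuated (by at most 0.017 in the threshold scenarios), and power falls by about 0 to 5 points at 52 weeks and 0 to 6 points at 156 weeks.

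The size rests on assumed trajectories, on threshold-triggered rescue as the event, and on event rates that the documents do not give. If 52-week events are few, the gain at step 5 is close to nil: +0.3 to +0.6 points at a 10% control rate with a baseline hazard ratio per SD of 1.3 to 1.6. The losses of 10 to 32 points in the wider check need common events together with a baseline effect stronger than the rescue thresholds produced, and the documents give no ground for expecting that.

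**What to change.** In SAP 7.5.4 and Protocol 8.4.2.2, state that the Cox model contains treatment and baseline HbA1c as a continuous covariate, for both the 52-week and 156-week analyses. Add time in days from first dose and Efron handling of ties as a harmless clarification. Label the hazard ratio as conditional on baseline HbA1c, keep the Kaplan-Meier curves unadjusted, and report the treatment-only Cox model as a sensitivity analysis.

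Timing: the change must be fixed before the relevant unblinding or lock. If the 52-week test has been run, its original analysis stands and the adjusted version is a sensitivity analysis. A change to the 156-week model must be dated and justified before final lock, with an acknowledgement that the 52-week data were already known to the sponsor.

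Cost: one sentence and one covariate. The hazard ratio becomes conditional, as the responder odds ratio already is. A subject without a baseline HbA1c drops out of the model, because the Randomized Subjects Data Set (SAP 6.3.3) does not require one, whereas the Full Analysis Set (SAP 6.3.4) does. Few if any should be lost: eligibility needs a central screening HbA1c, and SAP 7.1.1.1 takes the latest value up to the day of first dosing as baseline.
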